2. STUDY DESIGN

2.1. General Design

This is a multicenter, randomized, double-blind, parallel-group, placebo-controlled study with an open-label period to evaluate the efficacy, safety, and tolerability of monthly and quarterly sc fremanezumab compared with placebo in patients with chronic migraine (CM) and episodic migraine (EM) with inadequate response to prior preventive treatments.

The study will consist of a screening visit, a run-in period (28 days), a 12-week double-blind, placebo-controlled treatment period, a 12-week open-label period, and a follow-up visit 6.0 months after the last dose of fremanezumab for ADA blood sample collection.

At the end of the open-label treatment period (4 weeks after the last dose) an end of treatment study visit (visit 8) will be scheduled and patients should return to the care of their treating physicians. Patients should be treated with standard of care after withdrawal from or termination of the 24-week treatment period/study, as appropriate.

Double-blind period

At the baseline visit (visit 2), patients will be randomly assigned to a treatment group with fremanezumab (2 different dose regimens) or placebo in a 1:1:1 ratio as follows:

- For patients with CM:
 - sc administration of 675 mg of fremanezumab at visit 2 followed by monthly sc administration of 225 mg of fremanezumab for 2 months or
 - sc administration of 675 mg of fremanezumab at visit 2 followed by monthly sc administration of matching placebo for 2 months or
 - 3 monthly doses of matching placebo
- For patients with EM:
 - sc administration of fremanezumab at 225 mg plus 2 matching placebo injections as first dose followed by monthly sc administration of 225 mg of fremanezumab for 2 months or
 - sc administration of fremanezumab at 675 mg as first dose followed by monthly sc administration of matching placebo for 2 months or
 - 3 monthly doses of matching placebo

Randomization and treatment assignment for the double-blind period will be performed using electronic interactive response technology (IRT). The study will be stratified based on CM or EM, gender, country, and a special treatment failure group defined as patients who must have had inadequate response to valproic acid. In addition, patients in the special treatment failure group must have had inadequate response to 2 to 3 other classes of migraine preventive medications as defined in Appendix H of the study protocol.

The proportion of CM and EM patients in the study should be approximately 50:50 in each subgroup.

Statistical Analysis Plan

CM is defined as:

Patient fulfills the following criteria for CM in prospectively collected baseline information during the 28-day run-in period:

- Headache occurring on ≥ 15 days
- On ≥ 8 days, fulfilling any of the following:
 - ICHD-3 diagnostic criteria C and D for 1.1 Migraine without aura (Appendix U of the study protocol)
 - ICHD-3 criteria B and C for 1.2 Migraine with aura (Appendix U of the study protocol)
 - Probable migraine (a migraine subtype where only 1 migraine criterion is missing)
 - The patient used a triptan or ergot derivative to treat established headache.

EM is defined as:

The patient fulfills the following criteria for EM in prospectively collected baseline information during the 28-day run-in period:

- Headache occurring ≥ 6 days but < 15
- On ≥ 4 days, fulfilling any of the following:
 - ICHD-3 diagnostic criteria C and D for 1.1 Migraine without aura
 - ICHD-3 criteria B and C for 1.2 Migraine with aura
 - Probable migraine (a migraine subtype where only 1 migraine criterion is missing)
 - The patient used a triptan or ergot derivative to treat an established headache

Blinded treatment will be administered sc once a month (approximately every 28 days) for a total of 3 doses (visits 2,3, and 4)

Open-label period

After visit 4, all patients completing the double-blind period will enter the open-label period. All patients (CM and EM) will receive sc 225 mg of fremanezumab monthly for 3 months (visits 5, 6, and 7).

The open-label period will not be randomized as all patients will receive the same monthly dose (225 mg fremanezumab).

Open-label treatment will administered for a total of 3 doses (visits 5, 6, and 7). Final study assessments will be performed at visit 8 (end-of-treatment [EOT] visit), approximately 4 weeks after administration of last dose of fremanezumab.

Follow up period

A follow-up visit will be scheduled 6.0 months (> 5 half-lives) after the last study drug administration for ADA blood sampling. Patients who discontinue early will have the follow-up visit 6.0 months after the last dose.

The total duration of patient participation in the study is planned to be 50 weeks including a run-in period lasting 28 days, a double-blind treatment period lasting 12 weeks, an open-label period lasting 12 weeks, and 1 follow-up visit at week 46.

Patients are expected to complete the entire duration of the study, including the open-label period and the follow-up visit.

The end of study is defined as the last visit of the last patient (follow-up visit, visit 9). However, an interim database lock will occur following the end of the double-blind treatment period of the last patient for analysis of that portion of the study data. A second interim lock will occur following the end of the open-label period.

Study procedures and assessments with their timing are summarized in Table 2 of the study protocol.

2.2. Randomization and Blinding

The sponsor, investigators, study staff (except for staff involved in bioanalytical analyses), and patients will be blinded to treatment assignment during the double-blind period. A computer-generated master randomization list will be provided to drug packaging facilities. Packaging vendor(s) will package active drug and placebo into single-visit kits according to Good Manufacturing Practice procedures. Kits will be identical in appearance and contain 1 prefilled syringe with active drug or placebo. Adequate kit supply for upcoming study visits will be managed by IRT and kept (refrigerated at 2°C to 8°C) on site.

In this randomized study, the double-blind period will be stratified based on CM or EM, gender, country, and a special treatment failure group defined as patients who must have had inadequate response to valproic acid. In addition, patients in the special treatment failure group must have had inadequate response to 2 to 3 other classes of migraine preventive medications as defined in Appendix H of the study protocol.

Each patient will undergo randomization in a 1:1:1 ratio within the stratum to which he or she belongs to receive 1 of the 2 fremanezumab dose regimens or placebo, as assigned by the IRT. The IRT will manage initial drug supply, maintenance of adequate study drug supplies on site, and study randomization centrally. At the time of each study visit, the IRT will be queried, and site personnel will retrieve and administer a 1.5-mL volume from each syringe contained in the appropriately numbered kit(s).

2.3. Data Monitoring Committee

There will be no Data Monitoring Committee in this study.

2.4. Sample Size and Power Considerations

In the Phase 2b study for CM (study LBR-101-021), the treatment difference between 675/225/225 mg and placebo in change from baseline in monthly average migraine days was 2.1 days (standard deviation [SD]=5.2 days). In the phase 2b study for EM (study LBR-101-022), the treatment difference between 225 mg monthly dose and placebo in change from baseline in monthly average migraine days was 2.7 days (SD=4.1 days). In the Phase 3 study for CM (study TV48125-CNS-30049), the treatment differences to placebo in change from baseline in monthly average migraine days were 1.7 days and 1.8 days for the quarterly dose and the monthly dose, respectively (SD=5.4 days). In the Phase 3 study for EM (study TV48125-CNS-30050), the treatment differences to placebo in change from baseline in monthly average migraine days were 1.3 days and 1.5 days for the quarterly dose and the monthly dose, respectively (SD=3.4 days). Combining the information above, a treatment difference of 1.8 days is used. Considering the patient population is different from the previous studies, a SD of 6 days is used to account for the complexity and uncertainty of this study.

A sample size of 705 (235 patients per treatment group) evaluable patients completing the study is needed for 90% power to show a 1.8 difference in migraine days (assuming a common SD of 6 days) at an alpha level of 0.05. Assuming a 12% discontinuation rate, 268 patients per treatment group will be randomized in the study.

2.5. Sequence of Planned Analyses

2.5.1. Planned Interim Analyses

An interim analysis is planned when the last patient has completed the double-blind period. A second interim analysis is planned when the last patient has completed the open-label period. Final database lock will occur following the end of the follow-up period.

The inferential analysis of efficacy variables for comparison between each fremanezumab treatment group (monthly dose and quarterly dose) and placebo will be done at the time of the first interim lock. The appropriate method for type 1 error control will be applied to the first interim analysis.

Efficacy analysis for the open-label portion of this study is considered exploratory and mainly descriptive. This analysis will be done at the time of the second interim database lock.

2.5.2. Final Analyses and Reporting

All analyses identified in this SAP will be performed after the first interim database lock for the double-blind period and after the second interim database lock for the open-label period of this study as defined in the study protocol.

This SAP and any corresponding amendments will be approved before the first interim database lock, in accordance to SOP GBP_RD_702 (Statistical Analysis Plan).

The randomization codes will not be unblinded until this SAP has been approved and issued.

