5.9. Maintenance of Randomization and Blinding

5.9.1. Maintenance of Randomization

Patient randomization codes will be maintained in a secure location at the service provider contracted to generate the codes. At the time of the final analysis (after the end of study), after receiving unblinding request from Teva statistician, the service provider will provide the unblinded IMP assignment according to the processes defined in the relevant Standard Operating Procedure (SOP).

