7.1.2. Recording and Reporting of Adverse Events

For recording of adverse events, the study period is defined for each patient as the time period from signature of the informed consent form to the end of the follow-up period. The follow-up period of recording of adverse events is defined as 6.0 months after the last dose of IMP. The period for reporting treatment-emergent adverse events is defined as the period after the first dose of IMP is administered and until end of follow-up period.

All adverse events that occur during the defined study period must be recorded on the source documentation and the CRF, regardless of the severity of the event or judged relationship to the IMP. For serious adverse events, and protocol defined adverse events of special interest (see Section 7.1.7) the serious and protocol defined adverse event report form must be completed and the serious adverse event or protocol defined adverse event of special interest must be reported immediately (Section 7.1.5.3). The investigator does not need to actively monitor patients for adverse events once the study has ended. Serious adverse events and adverse events of special interest occurring in a patient after the defined study period should be reported to the sponsor if the investigator becomes aware of them, following the procedures described in Section 7.1.5.3.1.

At each contact with the patient, the investigator or designee must question the patient about adverse events by asking an open-ended question such as “Have you had any unusual symptoms or medical problems since the last visit? If yes, please describe.” All reported or observed signs and symptoms will be recorded individually, except when considered manifestations of a medical condition or disease state. A precise diagnosis will be recorded whenever possible. When such a diagnosis is made, all related signs, symptoms, and any test findings will be recorded collectively as a single diagnosis on the CRF and, if it is a serious adverse event, on the serious adverse event form.

The clinical course of each adverse event will be monitored at suitable intervals until resolved, stabilized, or returned to baseline; or until the patient is referred for continued care to a health care professional; or until a determination of a cause unrelated to the IMP or study procedure is made.

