
A secondary objective of the study is to evaluate the safety and tolerability of fremanezumab administered as monthly and quarterly sc injections to adult patients with migraine with inadequate response to 2 to 4 classes of prior preventive treatments as compared with placebo
	
Secondary safety/tolerability endpoints:
 
 ● occurrence of adverse events throughout the study ● clinical laboratory (serum chemistry, hematology, coagulation and urinalysis) test results at specified time points ● vital signs (systolic and diastolic blood pressure, oral temperature, and pulse rate) measurements at each visit. Note: In addition, oxygen saturation and respiratory rate will be measured in cases of suspected anaphylaxis and severe hypersensitivity ● 12-lead ECG findings at specified time points ● use of concomitant medication for adverse events during the study ● number (%) of patients who did not complete the study due to adverse events ● clinically significant changes in physical examinations, including body weight ● occurrence of severe hypersensitivity/anaphylaxis reactions ● suicidal ideations and behaviors as measured by the eC-SSRS

ECG=electrocardiogram; eC-SSRS= electronic Columbia-Suicide Severity Rating Scale; Test; sc=subcutaneous.

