8. SAFETY ANALYSIS

8.1. General

The safety analysis sets will be used for all safety analyses. Summaries will be presented separately for the double-blind treatment period and open-label treatment period. For the double-blind treatment period, summaries will be presented by migraine classification (ie, CM, EM, and all), treatment group and all fremanezumab, unless otherwise stated. For the open-label treatment period, summaries will be presented by migraine classification (ie, CM, EM, and all), double-blind treatment group (ie, placebo, fremanezumab 675 mg/placebo/placebo, fremanezumab 675/225/225 mg, fremanezumab 225/225/225 mg, all fremanezumab), and overall (ie, total).

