15. PLANNED INTERIM ANALYSIS

An interim analysis is planned when the last patient has completed the double-blind period. Final database lock will occur following the end of the open-label period.

The inferential analysis of efficacy variables for comparison between each fremanezumab treatment group (monthly dose and quarterly dose) and placebo will be done at the time of the first interim lock. The appropriate method for type 1 error control will be applied to the first interim analysis.

Efficacy analysis for the open-label portion of this study is considered exploratory and mainly descriptive. This analysis will be done at the time of the final database lock.

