17. CHANGES TO ANALYSES SPECIFIED IN THE STUDY PROTOCOL

The planned interim analyses (see Section 2.5.1) have been updated to indicate that there will be 2 interim database locks and a final database lock. This was updated as clarification.

The PP analysis set definition (see Section 3.4) has been modified to update “completing the study” to “completing the double-blind treatment period”. This change has been made as this analysis set is only used for the primary and secondary efficacy endpoints which are for the double-blind treatment period only. Additional details have also been added regarding compliance and incorrect study drug administered. A statement has also been added to clarify that a blinded data review meeting will be conducted prior to the interim database lock to determine the exclusion of the patients.

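### SAP 8.8 tabulates ECG change at month 4, where no ECG is scheduled, instead of month 3, and SAP 2.5.2 gives the final lock after follow-up no analysis to run

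*SAP*

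**What the plan says.** **ECG.** SAP 8.8 counts normal/abnormal shifts by visit and for each patient's worst postbaseline finding. It summarises numeric values and changes from baseline at month 4, the end of treatment visit and the last on study assessment. Another sentence promises summary statistics for ECG variables without naming visits. SAP 8.1 governs all safety output: "Summaries will be presented separately for the double-blind treatment period and open-label treatment period". Protocol Table 2 and Appendix B schedule ECGs at screening, baseline, visit 5 (month 3) and visit 8 (end of treatment or early termination).

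**Locks.** SAP 2.5.1 plans two interim analyses and then states: "Final database lock will occur following the end of the follow-up period". SAP 17 confirms that "there will be 2 interim database locks and a final database lock". SAP 15 still reads: "Final database lock will occur following the end of the open-label period". SAP 2.5.2, the section on final analyses, has every analysis in the SAP "performed after the first interim database lock for the double-blind period and after the second interim database lock for the open-label period".

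**Data that run past the second lock.** In Protocol 7.1.2 the reporting window for "treatment-emergent adverse events is defined as the period after the first dose of IMP is administered and until end of follow-up period". SAP Table 1 lists "occurrence of adverse events throughout the study" as a secondary safety endpoint, and SAP 8.3 summarises all treatment-emergent events. SAP 5.2 counts patients who complete or withdraw from the study. SAP 8.10 takes concomitant medication to the end of the study, which SAP 2.1 places at the last patient's visit 9.

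**The concern.** A programmer who follows SAP 8.8 as written builds a numeric ECG row at a visit without a scheduled ECG, and builds none for the one scheduled postbaseline visit where drug and placebo can be compared concurrently. ECG findings are a secondary safety endpoint.

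A programmer who follows SAP 2.5.2 as written runs the safety and disposition tables for the last time at the second lock, while some patients are still in follow-up. Events that the protocol counts as treatment-emergent would reach the database afterwards with no planned summary run. Tables on study completion and on medication to the end of the study would be reported before those data were complete.

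**Working it through.** **ECG: schedule against table rows**

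| Visit | ECG scheduled (Protocol Table 2, Appendix B) | Named for numeric values and changes (SAP 8.8) |
|---|---|---|
| Visit 5, month 3, day 84 | yes, before the first open-label dose | no |
| Visit 6, month 4, day 112 | no | yes |
| Visit 8, end of treatment, day 168 | yes | yes |

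SAP 8.8 therefore names 1 of the 2 scheduled postbaseline ECG visits, plus one visit with none. A different labelling convention does not explain this. SAP 8.5 lists months 3 and 4 separately for laboratory tests, matching visits 5 and 6 in Table 2. SAP 8.6 says month 3 for physical examination, which has the same visits as ECG. Early-termination ECGs cannot fill the month-4 row, because SAP 4.4 keeps them out of by-visit summaries; only unscheduled ECGs could. Protocol 9.7 asks for changes at each time point, but the SAP Introduction gives the SAP precedence where the two differ. Protocol 3.1 expects 705 completers, 235 per group, so visit 5 should hold roughly that many ECGs.

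**Locks: how much follow-up falls after them**

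Inputs: last open-label dose on day 140, visit 8 on day 168±5 and visit 9 on day 320±15 (Table 2); follow-up of 180 days after the last dose (Protocol 4.3).

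1. Schedule check: 140 + 180 = 320, which reproduces the visit 9 day.
2. Last patient: 320 − 168 = 152 days from visit 8 to visit 9, and 152/320 = 47.5% of the planned time after first dose. With the windows: (320 − 15) − (168 + 5) = 132 and (320 + 15) − (168 − 5) = 172 days.
3. Earlier patients: someone randomised *r* days before the last patient has 152 − *r* days of follow-up after the event that triggers lock 2, and none once *r* reaches 152.
4. Double-blind withdrawals: a last dose on day *d* = 0, 28 or 56 ends follow-up on day *d* + 180 = 180, 208 or 236. Lock 1 is triggered by the *last* patient's day 84, so the time left after it is *d* + 180 − 84 − *r* = *d* + 96 − *r*. Only withdrawals randomised within 96, 124 or 152 days of the last patient are exposed.

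**Illustration under assumed accrual.** The documents give no accrual rate. Assume uniform enrolment and no delay before the lock. About 2 years (104 weeks) in total, less 50 weeks per patient, leaves 54 weeks, or 378 days, of enrolment. Then 152/378 = 40% of patients have some follow-up after lock 2. The mean over all patients is 152²/(2 × 378) = 30.6 days, and 30.6/320 = 9.6%. If the planned calendar period means 21 to 27 months (91 to 117 weeks), enrolment is 41 to 67 weeks (287 to 469 days). The mean is then 152²/(2 × 287) = 40.3 down to 152²/(2 × 469) = 24.6 days, or 12.6% down to 7.7%. Any lag before the lock lowers these figures.

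**The case against.** On ECG, the other side would call this a one-word slip with little effect. Month-3 ECGs remain in the by-visit shifts and the worst-finding summary. The sentence on summary statistics for ECG variables has no visit restriction and may cover them. Since 8.1 requires separate double-blind output, the last on study assessment can be read within that period, and would then be visit 5 for completers. This limits the harm, but the named row is still wrong, and the SAP does not define the last assessment by period.

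On the locks, silence is not exclusion. SAP 2.5.2 does not forbid a later run, SAP 5.2 and 8.10 can be completed only after follow-up, and Protocol 5.9.1 mentions a final analysis after the end of study. Serious events and events of special interest are reported as they occur, and deaths receive narratives. A final update is therefore probably intended. The SAP still gives it no content, and 2.5.2 ties the second lock to the open-label period.

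A reader might infer that follow-up events belong to no period and could be placed in either. The documents do not support that. Under SAP 3.3 a patient who left before open-label dosing is only in the double-blind safety set. For a patient dosed open-label, every follow-up event comes after an open-label dose. Protocol 7.1.2 makes both treatment-emergent. What is missing is one explicit sentence.

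**Conclusion.** Both parts hold, as specification errors in descriptive safety output that should be corrected. The ECG row directly contradicts the visit schedule. The lock gap leaves three sets of summaries incomplete if 2.5.2 is followed literally. Its size is at most 152 planned days, for the last patient, and falls day for day for patients randomised earlier. Under the assumed uniform accrual the mean is about 25 to 40 days per patient. The number of events affected cannot be derived from the documents.

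Three stronger readings should be avoided:

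- Month-3 ECG data are not lost; only the named numeric row is missing.
- The 47.5% is not a typical loss, and the 96, 124 and 152 days are not the loss for each withdrawal. A patient who enrolled early and withdrew finishes follow-up before lock 1 and loses nothing.
- The leftover wording in SAP 15 does not abolish the lock after follow-up; SAP 17 largely settles that.

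Efficacy inference is done at the first interim lock, so neither it nor alpha is touched.

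**What to change.** - SAP 8.8: replace month 4 with month 3, to match Protocol Table 2. This is free.
- SAP 2.5.2: assign a rerun of the summaries in 5.2, 8.3 and 8.10, with their listings, to the final lock. This costs one extra set of descriptive tables and needs no new data.
- Minor clarification in SAP 8.1 and 8.3: say that follow-up events are included and count under the period of the patient's last dose, as 3.3 already implies.
- Editorial: align SAP 15 with 2.5.1 and 17.
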